e) Assessment Measures & Administration Schedule: All baseline measures will be administered as part of screening through the HARP studies (described above). The following list specifies the assessment measures we propose to collect at follow-up assessments, with assessments conducted at both 3 and 6 month follow-up unless otherwise specified:

Domain 1, Social connectedness: Loneliness scales (UCLA Loneliness Scale and DeJong Loneliness Scale); Berkman-Syme Social Network, Unidimensional Relationship Closeness Scale, *PROMIS social functioning* computerized adaptive tests (satisfaction with roles/activities, social isolation, meaning/purpose, companionship, emotional support, instrumental support).

Domain 2, Caregiving: *Montgomery Borgatta Caregiver Burden Scale*, Modified Caregiver Strain Index (MCSI), Caregiver Reaction Scale

Domain 3, Health indicators: WHODAS, PROMIS computerized adaptive tests of depression, anxiety, fatigue and pain interference; Modified Cornell Services Index (only 3 month); Neuropsychiatric Inventory (only 3 month), FAST (only 3 month) Modified Barthel Index (only 3 month), Columbia Suicide Severity Rating Scale (only 3-month).

Domain 4, Well-being indicators: WHOQOL-BREF is a 36-item measure of several domains of health related quality of life

Domain 5, Mechanisms of behavior/social connectedness change. *Interpersonal Needs Questionnaire (INQ)*; the PSS-10 measures perceived stress.

Domain 6, Feedback about intervention

Participations will be provided an opportunity to discuss what they liked and did not like about the intervention, including what aspects they found helpful. This part of the 3 month interview will be recorded on Zoom. A short self-administered feedback questionnaire will be completed at 6 month follow-up.

f) Study Conditions: This study is a single-arm clinical trial of Social Engage psychotherapy. [name] conducted a study at URMC (K23MH096936) using Social Engage psychotherapy that demonstrated increases in well-being and social engagement for lonely older adults. Social Engage psychotherapy involves psychoeducation on the importance of social connections for health as well as structured goal setting for increasing social

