Aim 3 is to obtain evidence for a signal for efficacy with regards to social connectedness. Baseline data from the assessment battery will be used: a behavioral indicator of social connectedness (quality and quantity of positive social interactions), a psychological indicator of connectedness (loneliness), mechanisms of change (autonomy, competence, and relatedness), and indicators of well-being (psychological distress and quality of life). Assessments will be completed at the end of intervention (3 months), and 6-month follow-up. Follow-up data will be used to estimate the length of treatment needed to demonstrate improvement and to estimate the proportion of participants who demonstrate increases in social connectedness by the end of the intervention and the proportion who maintain gains after the intervention. Our hypotheses will be tested with repeated measures ANOVAs with the Stata software package; significant increases support a signal for efficacy.

h) Data and Safety Monitoring Plan: See Data and Safety Monitoring Plan document.

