Engage Psychotherapy to Promote Connectedness in Caregivers

NCT04176601

Statistical Analysis Plan

6/30/2019

P30AG064103-Pilot2

Statistical Design & Power: Study 2

We will enroll n=30 participants, anticipating n=24 will begin the intervention (considering exclusion criteria, interest in the intervention) and a conservative potential attrition rate of 20% (15% is more likely based on the PIs' prior studies). Based on our prior RCT of Engage—including its flexible structure (e.g., accommodating phone sessions when needed) and high acceptability—we expect most participants will complete a full course of Social Engage (i.e., at least 6 sessions out of 8 allowed; we had 88% achieve this in our prior Engage study). We have also successfully retained caregivers in our intervention research. For [name] clinical trials, one of which includes an 8-week home-based computer intervention, and the other a 9-session in-person mindfulness group training (i.e., requiring attendance at a local community site), attrition rate continues to be very low, ~10%. Given these considerations, we anticipate n=20 participants will provide follow-up data and complete a full course of Social Engage. This calculation includes our expected recruitment rate (n=4 per month), projections about the length of time between enrollment and commencement of therapy (1-2 weeks), amount of time to complete the intervention (maximum of 3 months, including two weeks buffer for missed sessions), and time to complete follow-up assessments. Given start-up and time for data analysis, our study resources and recruitment infrastructure will support running our participants through all study procedures within the 1-year timeline.

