Participants will be characterized at baseline with regards to demographic characteristics, degree of social disconnectedness, caregiver distress, well-being (depressive symptoms, quality of life), cognitive function, and relationship satisfaction with the person they care for. For Aim 1 the number of subjects and the number of sessions completed by each will be examined to determine if at least 80% of subjects will be willing to start Social Engage and at least 75% complete a full dose of the intervention. Aim 2 is to determine the most useful barrier strategies to use with caregivers. We will tabulate how often each strategy is used within and across participants. Qualitative analyses will be conducted with interview data from participants at follow-up regarding their perceptions of effective barrier strategies (Aim 2) and effective/ineffective aspects of the therapy in general (Aim 3). Aim 3 is to obtain evidence for a signal for efficacy with regards to social connectedness. Baseline data from the STAR core battery will be used: a behavioral indicator of social connectedness (quality and quantity of positive social interactions), a psychological indicator of connectedness (loneliness), mechanisms of change (autonomy, competence, and relatedness), and indicators of well-being (psychological distress and quality of life). Assessments will be repeated after 1 month, the end of intervention (3 months), and at 6-month follow-up. Follow-up data at one month will be used to estimate the length of treatment needed to demonstrate improvement; follow-up data at the end of treatment will be used to estimate the proportion of participants who demonstrate increases in social connectedness by the end of the intervention; and follow-up data at 6-months will be used to demonstrate the proportion of participants who maintain gains in connectedness after completing the intervention (and interacting with the study therapist).

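### The Aim 3 repeated measures ANOVA has no missed-visit rule, so caregivers with only a baseline score add nothing and mean change can be biased; a mixed model using all starters is a cheap improvement

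*Protocol*

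**What the plan says.** The only Aim 3 test is in Protocol III.g: "Our hypotheses will be tested with repeated measures ANOVAs with the Stata software package", with a significant rise read as a sign of efficacy. The same section sets the follow-up times: "Assessments will be completed at the end of intervention (3 months), and 6-month follow-up". Protocol III.e agrees, "with assessments conducted at both 3 and 6 month follow-up unless otherwise specified", and places baseline before therapy: "All baseline measures will be administered as part of screening through the HARP studies".

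The SAP (Statistical Design & Power: Study 2) states "We will enroll n=30 participants, anticipating n=24 will begin the intervention" and allows for "a conservative potential attrition rate of 20" per cent, with 15% thought more likely. It expects 20 participants with follow-up data. It names no test for Aim 3, and its schedule has one more visit than the Protocol's: "Assessments will be repeated after 1 month, the end of intervention (3 months), and at 6-month follow-up".

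Neither document states how a missed visit is handled, which form of the ANOVA is meant, what covariance is assumed, whether a sphericity correction applies, or what alpha is used.

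**The concern.** The plan expects to lose roughly four of 24 starters, and its named method makes poor use of them. Because baseline is collected at screening, someone lost before 3 months will normally have a baseline score and nothing else. A complete-case ANOVA drops that person. A long-format ANOVA keeps the row, but the subject effect absorbs the single score, so it says nothing about change.

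This matters if loss is related to loneliness. That is plausible here, because participants are selected for distress and loneliness and the 6-month contact is remote with a smaller payment ($30 against $60). Caregivers who start loneliest have the most room to regress, so losing them shifts the mean change among those who remain. Aim 3 estimates are meant to inform a later randomized trial, so a shift in either direction carries forward.

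A secondary matter is that the uncorrected F-test needs sphericity. One visit before therapy and two after it make that doubtful.

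**Working it through.** **1. The plan's own figure.** 24 × (1 - 0.20) = 19.2 and 24 × (1 - 0.15) = 20.4. Both agree with the planned 20. The documents give no power, SD, effect size or alpha for Aim 3, so there is nothing further to reproduce.

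**2. Assumed inputs.** Loneliness is in SD units and higher is worse. True change is -0.30 at 3 and 6 months. Correlations are 0.5 (0 with 3 months), 0.5 (0 with 6) and 0.8 (3 with 6). Dropout is logistic, with slope 0.5 to 1.5 per SD. Alpha is 0.05.

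**3. Both follow-ups lost, depending on baseline (18%).** With baseline mean zero, the expected change given baseline Y0 is -0.30 - (1 - ρ)Y0. If the retained group has baseline mean m, the observed mean change is -0.30 - (1 - 0.5)m. At slope 1, m is about -0.16:

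-0.30 + 0.5 × 0.16 = -0.22.

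The likelihood estimate evaluates the same regression at the baseline mean of all starters, which returns -0.30. Both ANOVA forms give the same answer here, because baseline-only records carry no within-person contrast.

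**4. Only the 6-month visit lost, depending on the 3-month score (22%, slope 1).** Complete-case analysis discards the 3-month score as well. Long format keeps it.

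| Dropout | Complete-case, 3 / 6 months | Long-format, 3 / 6 months | Likelihood |
|---|---|---|---|
| Baseline-driven, slope 0.5 | -0.26 / -0.26 | same | -0.30 |
| Baseline-driven, slope 1 | -0.22 / -0.22 | same | -0.30 |
| Baseline-driven, slope 1.5 | -0.20 / -0.20 | same | -0.30 |
| 3-month-driven, slope 1 | -0.39 / -0.36 | -0.30 / -0.31 | -0.30 |

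**5. A second set of assumptions** (24 starters, about 17% loss, true change -0.50 SD, correlation falling with time, 0.5 to 0.7 over 3 months, slope 1.5) shows the same pattern.
- Baseline-driven loss: either ANOVA form gives -0.40 to -0.44 at 3 months and -0.36 to -0.40 at 6 months. Likelihood gives -0.50.
- Loss of the 6-month visit driven by change at 3 months: complete-case gives -0.65 to -0.69 and -0.63 to -0.65. Long-format gives -0.50 and -0.55. Likelihood gives -0.50.

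**6. Bias against sampling error.** At slope 1 in step 3, the standard error of the mean change is √[2(1 - 0.5)/(24 × 0.82)] = √(1/19.68) = 0.225. The bias of 0.08 is 0.08/0.225 = 0.36 standard errors. A nominal 95% interval would cover about 93.5%.

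**7. The F-test, n = 20, visits at 0, 3 and 6 months.** Correlations that decay with time (0.3 to 0.9 over 3 months) give a true error of 5.2% to 5.8%, or 6.0% if the SD also rises over time. The 0.5/0.5/0.8 correlations (epsilon 0.80) give about 6%. In the time-decay scenarios, Greenhouse-Geisser brings the error to 4.6% to 4.9%.

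**The case against.** The strongest reply is that this is a single-arm, early-stage development study looking for a signal. With about 20 people, sampling error exceeds the bias (step 6). Part of the bias depends on how the ANOVA is run: when only the 6-month visit is missed, long-format ANOVA is nearly unbiased. The wording does not rule out a sphericity correction, which would remove the p-value problem without a new model. Aim 3 also seeks proportions who respond and who maintain gains, which a mean-change model does not supply. All of this stands, and it keeps the point at the level of a recommended improvement. It does not rescue the case in step 3, where both ANOVA forms fail and a sphericity correction does nothing.

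Three stronger readings are tempting, and the documents do not support them.
- A reader might infer that unequally spaced visits invalidate the ANOVA. The document that names the ANOVA has visits at 0, 3 and 6 months, which are nominally equally spaced. Only the earlier-dated SAP has a 1-month visit, and it names no test. The condition that matters is sphericity, which can fail at equal spacing too.
- A reader might apply 15% loss independently at each visit: 24 × 0.85² = 17.3 complete on two follow-ups and 24 × 0.85³ = 14.7 on three. The SAP uses its percentage as overall attrition leading to 20 with follow-up data, so compounding it contradicts the plan.
- A reader might infer that any mixed model removes the bias. A random-intercept model keeps the equal-correlation assumption, and no mixed model corrects loss that depends on unseen scores.

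**Conclusion.** The point holds, with dropout as its main ground. The plan names a method that gains nothing from baseline-only caregivers, expects 15% to 20% attrition, and has no rule for it. Under the assumptions in step 2, baseline-driven loss shrinks a true -0.30 SD to between -0.26 and -0.20 in either ANOVA form. If loss follows the 3-month score and the analysis is complete-case, the benefit is exaggerated instead, to about -0.39 at 3 months and -0.36 at 6 months. An unstructured likelihood-based model returns -0.30 in both, on the condition that missingness depends only on observed scores.

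The p-value effect on the Protocol schedule is about one percentage point or less and is minor.

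The correlations, true change, dropout slopes and alpha are all assumed. The baseline was also simulated without the truncation that the loneliness entry threshold (UCLA score above 6) imposes, so the figures show direction and order of size and are not forecasts.

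**What to change.** Replace the ANOVA sentence in Protocol III.g, and put the same text in the SAP:

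*Mean change in each continuous Aim 3 outcome will be estimated with a linear mixed model (Stata mixed, REML, Kenward-Roger degrees of freedom) with visit as a categorical effect and an unstructured within-person covariance. All observed scores from every participant who starts therapy will be used, including those with baseline only. Mean changes from baseline will be reported with 95% confidence intervals. If the model does not converge, the named fallback covariance will be used. Validity requires that missingness depends only on observed scores.*

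Name the fallback now, for example heterogeneous compound symmetry, or in Stata a random intercept with a separate residual variance for each visit.

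Separately, reconcile the SAP's 1-month assessment with the Protocol, which does not have it, so that the visits in the model are defined.

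The cost is wording in two documents, with the same software and data and no added burden on participants. The statistical price is a small loss of degrees of freedom for the unstructured covariance.

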Engage Psychotherapy to Promote Connectedness in Caregivers

NCT04176601

Statistical Analysis Plan

6/30/2019

P30AG064103-Pilot2

Statistical Design & Power: Study 2

We will enroll n=30 participants, anticipating n=24 will begin the intervention (considering exclusion criteria, interest in the intervention) and a conservative potential attrition rate of 20% (15% is more likely based on the PIs' prior studies). Based on our prior RCT of Engage—including its flexible structure (e.g., accommodating phone sessions when needed) and high acceptability—we expect most participants will complete a full course of Social Engage (i.e., at least 6 sessions out of 8 allowed; we had 88% achieve this in our prior Engage study). We have also successfully retained caregivers in our intervention research. For [name] clinical trials, one of which includes an 8-week home-based computer intervention, and the other a 9-session in-person mindfulness group training (i.e., requiring attendance at a local community site), attrition rate continues to be very low, ~10%. Given these considerations, we anticipate n=20 participants will provide follow-up data and complete a full course of Social Engage. This calculation includes our expected recruitment rate (n=4 per month), projections about the length of time between enrollment and commencement of therapy (1-2 weeks), amount of time to complete the intervention (maximum of 3 months, including two weeks buffer for missed sessions), and time to complete follow-up assessments. Given start-up and time for data analysis, our study resources and recruitment infrastructure will support running our participants through all study procedures within the 1-year timeline.

This is a Stage One (NIH Stage Model) intervention development study. Aim 1 examines feasibility of Social Engage psychotherapy for caregivers; Aim 2 explores which behavioral strategies are most useful for caregivers when completing Social Engage psychotherapy; Aim 3 is to examine potential efficacy of Engage by examining satisfaction with the intervention and changes in social connectedness over the course of therapy. For Aim 3, we will measure a behavioral indicator of connectedness (quality and quantity of positive social interactions), a psychological indicator of connectedness (loneliness), and indicators of well-being at baseline, 1 month, end of treatment (3 months), and 3 months after completing treatment (6 month follow-up) to estimate the length of treatment needed for improvement; to estimate the proportion of participants who respond to treatment; and to examine the durability of the effect (to inform a fully powered, randomized efficacy trial).

Participants will be characterized at baseline with regards to demographic characteristics, degree of social disconnectedness, caregiver distress, well-being (depressive symptoms, quality of life), cognitive function, and relationship satisfaction with the person they care for. For Aim 1 the number of subjects and the number of sessions completed by each will be examined to determine if at least 80% of subjects will be willing to start Social Engage and at least 75% complete a full dose of the intervention. Aim 2 is to determine the most useful barrier strategies to use with caregivers. We will tabulate how often each strategy is used within and across participants. Qualitative analyses will be conducted with interview data from participants at follow-up regarding their perceptions of effective barrier strategies (Aim 2) and effective/ineffective aspects of the therapy in general (Aim 3). Aim 3 is to obtain evidence for a signal for efficacy with regards to social connectedness. Baseline data from the STAR core battery will be used: a behavioral indicator of social connectedness (quality and quantity of positive social interactions), a psychological indicator of connectedness (loneliness), mechanisms of change (autonomy, competence, and relatedness), and indicators of well-being (psychological distress and quality of life). Assessments will be repeated after 1 month, the end of intervention (3 months), and at 6-month follow-up. Follow-up data at one month will be used to estimate the length of treatment needed to demonstrate improvement; follow-up data at the end of treatment will be used to estimate the proportion of participants who demonstrate increases in social connectedness by the end of the intervention; and follow-up data at 6-months will be used to demonstrate the proportion of participants who maintain gains in connectedness after completing the intervention (and interacting with the study therapist).
